## **9.4 Assessment of Feasibility of Recruitment and Retention**

The feasibility of recruiting and randomizing ambulatory middle-aged and older women with incontinence into a randomized controlled trial of a yoga therapy versus physical conditioning program will be examined by monitoring the average number of participants recruited and randomized per month and per recruitment wave. The study team will also track the success rate of various recruitment approaches (fliers,

print notices, newspaper ads, etc.) and monitor the costs of recruitment per participant in order to guide future recruitment efforts. The investigators plan to recruit and randomize 15 to 30 women in each 3-month enrollment wave to confirm the feasibility of assembling a class size of 8 to 15 women per group per wave in a future full-scale trial.

The study team will also monitor participant retention rates during both the 12-week treatment period and the 12-week post-treatment follow-up period of the trial. Drop-out rates in both treatment groups are expected to increase over time (i.e., to be greater at 12 weeks than at 8 weeks or 4 weeks), but remain within acceptable parameters at 12 weeks of treatment and 12 weeks of post-treatment follow-up. If drop-out is substantial, the study team will conduct exploratory pooled logistic regression analyses to identify participant characteristics associated with drop-out.

The following parameters will be used to measure the adequacy of retention:

	During the 12-week intervention	12 weeks post-intervention
Optimal	< 10%	< 20%
Expected	< 15%	< 25%
Acceptable	< 20%	< 30%

## 9.5 Assessment of Adherence to Interventions

The study team will assess the feasibility of maintaining participant adherence to group classes and home practice by tracking the number and percentage of participants in each intervention group who complete at least 75%, 80%, and 90% of the recommended group classes as well as 75%, 80%, and 90% of the recommended home practice hours during the 12-week treatment period. During the 12-week post-treatment follow-up period, the study team will also track the number and percentage of participants who complete 25%, 50%, and 75% of recommended home practice hours; however, it should be noted that the study intervention is designed to be a self-contained 12-week intervention, in which sustained practice of yoga therapy or stretching/ strengthening exercises after the end of classes is encouraged but not considered mandatory. If appropriate, exploratory regression analyses will be used to identify participant characteristics associated with adherence to group classes and home practice.

The following parameters will be used to measure the adequacy of adherence:

	Attendance at group sessions during the 12-week intervention	Completion of home practice hours during the 12-week intervention	Completion of home practice hours post-intervention*
Optimal	≥ 90%	≥ 90%	≥ 75%
Expected	≥ 80%	≥ 80%	≥ 50%
Acceptable	≥ 75%	≥ 75%	any

\*Practice of yoga or stretching/strengthening exercises at home after 12 weeks, while desirable and encouraged, will not be considered mandatory to study success.

## 9.6 Interim Analyses and Stopping Guidelines

*Interim analyses and/or stopping for unexpected efficacy:* As this is a pilot study that is not powered to prove or disprove any hypotheses regarding efficacy, no formal interim analyses to evaluate efficacy will be performed. Given the short duration of treatment and small size of the study, the investigators believe that there is no scientific or ethical reason to stop the trial early or alter the trial design if treatment appears to be more effective than expected. Thus, as long as no safety issues arise, the trial will not be stopped or altered if the therapeutic intervention appears unexpectedly effective.

*Interim analyses and/or stopping for harm:* Although this study involves a low-impact behavioral intervention that is not expected to pose a significant risk to participant safety, consideration may be given to stopping the trial early if unexpected and clinically significant adverse effects occur in either treatment group that may endanger the safety of participants. These may take the form of SAEs or non-serious AEs posing a substantial safety risk and warranting early termination of the trial. If evidence of adverse effects emerges, the investigators in consultation with the DSM may determine that these side effects are minor and the study can continue as planned, or may decide to alter or stop the study to prevent these side effects. Because the sample is small, and preservation of the nominal type-I error rate is less important for safety than for efficacy, no formal interim analysis procedures are proposed.

*Interim analyses and stopping for futility:* Consideration may be given to stopping the trial if recruitment and retention are so poor that the ability to meet recruitment goals or meet retention thresholds is severely compromised. For example, consideration will be given to stopping this study prior to its scheduled completion if recruitment falls more than 30% below planned rates and/or timely follow-up (i.e., completion of study visits within recommended windows) falls below 70%.

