## 1. STUDY OBJECTIVES

**Aim 1: To examine the feasibility of recruiting and retaining ambulatory women aged 50 years and older into a randomized trial of a yoga therapy versus physical conditioning program for treatment of incontinence, and explore potential differences in retention and adherence by duration of treatment and follow-up.**

Expected outcome 1: We expect to recruit and randomize 15 to 30 women in each 3-month enrollment wave to confirm our ability to assemble a class size of 8 to 15 women per group per wave in a future full-scale trial.

Expected outcome 2: We expect drop-out rates in both treatment groups to increase over time, but remain <20% after 12 weeks of treatment and <30% at 12 weeks of post-treatment follow-up.

Expected outcome 3: We expect adherence to decrease over time, but remain >75% at 12 weeks of treatment (for group classes and home practice) and >50% at 12 weeks post-treatment (for home practice only).

**Aim 2: Explore whether a clinically meaningful reduction in incontinence frequency could be detected in a full-scale trial of yoga versus physical conditioning, and examine potential differences in treatment efficacy by duration of treatment and follow-up.**

Expected outcome 1: We will collect data on the standard deviation, intra-class correlation, and between-group difference in change in incontinence frequency to guide sample size projections for a future full-scale trial powered to detect a 25% greater reduction in incontinence frequency associated with yoga therapy.

Expected outcome 2: We will examine time-related trends in treatment effects on incontinence frequency to guide expectations of treatment efficacy over 8 versus 12 weeks of treatment as well as persistence of treatment benefits after 12 weeks of post-treatment follow-up in a future full-scale trial.

**Aim 3: Explore potential effects of yoga versus physical conditioning on other symptom and quality-of-life outcomes associated with incontinence and examine potential differences in treatment efficacy by duration of treatment and follow-up.**

Expected outcome 1: We will collect data on standard deviations, intra-class correlations, and between-group differences for changes in anxiety, depression, and quality-of-life questionnaire scores to guide estimates of minimum detectable effects for these secondary outcomes in a future full-scale trial.

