## 9.7 Outcomes

### 9.7.1 Feasibility Outcomes

The feasibility of recruiting and randomizing middle-aged and older women with urinary incontinence into a randomized trial of yoga therapy versus physical conditioning will be examined by calculating the average number of participants recruited and randomized per month and per recruitment wave. It is assumed that the study team will need to recruit and randomize 15 to 30 women in each 3-month enrollment wave to confirm ability to assemble a class size of 8 to 15 women per group per wave in a future full-scale trial.

The feasibility of retaining participants in this trial design will be assessed by monitoring rates of drop-out or loss-to-follow-up over 8 and 12 weeks of treatment as well as during the 12-week post-treatment follow-up period. Drop-out rates in both treatment groups are expected to increase over time (i.e., to be greater at 12 weeks than at 8 weeks), but remain less than 20% after 12 weeks of treatment and less than 30% at 12 weeks of post-treatment follow-up.

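### Does the 70% timely follow-up trigger for futility conflict with the trial's own acceptable drop-out of under 30%?

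*Combined protocol and SAP*

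**What the plan says.** Section 9.6 (futility paragraph) allows the trial to be stopped if recruitment and retention are so poor that "the ability to meet recruitment goals or meet retention thresholds is severely compromised". By way of example, "consideration will be given to stopping this study prior to its scheduled completion" if recruitment is more than 30% below plan and/or "timely follow-up (i.e., completion of study visits within recommended windows) falls below 70" per cent. It does not give the denominator, the visit or the time at which this share is judged.

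Section 9.4 introduces its retention table with "The following parameters will be used to measure the adequacy of retention". The first limit in each row is for drop-out during the 12-week intervention and the second for drop-out 12 weeks afterwards. Two rows matter here: "Expected < 15% < 25" per cent and "Acceptable < 20% < 30" per cent. The sentence before the table says that drop-out should rise over time but stay inside acceptable limits.

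Aim 1 (Expected outcome 2) expects drop-out to "remain <20% after 12 weeks of treatment and <30% at 12 weeks of post-treatment follow-up". Section 9.7.1 repeats this: "remain less than 20% after 12 weeks of treatment and less than 30% at 12 weeks of post-treatment follow-up".

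The windows in section 6.2.5 are days 50 to 62 for week 8 and days 78 to 90 for week 12. For the week-24 telephone and mail-in assessment there is only an upper limit, day 189, set to allow time for the post.

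**The concern.** Timely visits are a subset of completed visits. If timely follow-up is a share of all randomized women, every drop-out lowers it and every late visit lowers it further. The trigger sits at 70% and acceptable week-24 drop-out runs up to 30%, so nothing is left for lateness at the limit. The same data could then be rated acceptable under section 9.4 and put forward for possible stopping under section 9.6. Retention is an Aim 1 question, and the monitor must state after each review whether the study should continue, so a muddled threshold could matter.

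The second worry is the word expected. Drop-out of 17% at 12 weeks is within the expectation of Aim 1 and section 9.7.1 (under 20%), but misses the row labelled Expected in section 9.4 (under 15%).

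**Working it through.** **Inputs.** The 70% trigger (section 9.6); acceptable drop-out under 20% and under 30%, and Expected-row drop-out under 15% and under 25% (section 9.4); up to 90 women (section 9.2). On-time shares of 90% and 95% are assumptions, since the documents give none. The plan offers no derivation of the 70%; it equals 1 − 0.30, the complement of the acceptable week-24 limit.

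**Denominator: all randomized women.** Timely share = (1 − drop-out) × on-time share among the retained. The on-time share needed to stay at 70% is 0.70 / (1 − drop-out).

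| Drop-out | On-time share needed | Lateness allowed |
|---|---|---|
| 30% (acceptable limit, week 24) | 0.70/0.70 = 100% | 0% |
| 29% | 0.70/0.71 = 98.6% | 1.4% |
| 25% (Expected row, week 24) | 0.70/0.75 = 93.3% | 6.7% |
| 20% (acceptable limit, week 12) | 0.70/0.80 = 87.5% | 12.5% |
| 15% (Expected row, week 12) | 0.70/0.85 = 82.4% | 17.6% |

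In whole women at N = 90, the trigger needs 62 or fewer timely (62/90 = 68.9%; 63/90 = 70.0%).

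- Week 24, 26 drop-outs (28.9%): 64 retained, so 2 late women are enough.
- Week 24, 22 drop-outs (24.4%): 68 retained, so 6 late women are enough.
- Week 12, 17 drop-outs (18.9%): 73 retained, so it takes 11 late women (15.1% of those retained).

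**Chance of an observed share below 70% (binomial).**

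- Week 24, 25% drop-out, 95% on time: true share 0.75 × 0.95 = 71.25%; chance about 35% for n = 20 to 90.
- Week 24, 25% drop-out, 90% on time: true share 0.75 × 0.90 = 67.5%; chance 49% (n = 20) to 65% (n = 90).
- Week 12, 15% drop-out, 95% on time: true share 0.85 × 0.95 = 80.75%; chance 7% (n = 20) and 0.5% (n = 90).

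The first case puts the true share 1.25 points above the cut-off, so frequent crossing is built in. It also takes drop-out at the edge of the Expected row, which is an upper bound.

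**Denominator: women still in follow-up.** Drop-out does not enter. The trigger fires only if more than 30% of the retained women are outside their windows, and the overlap disappears.

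**Everyone retained on time.** Drop-out below 30% gives a timely share above 70%, and the trigger does not fire.

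**The two expected values.** The limits are nested: drop-out under 15% is also under 20%, and under 25% is also under 30%. The sentence before the section 9.4 table states the expectation as staying within acceptable limits, and the Acceptable row is 20% and 30%. Aim 1 and section 9.7.1 put those numbers into the same sentence. The Expected row is a finer grade inside that ceiling.

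**The case for a change.** The best argument for a change is that all randomized women is a natural denominator here. Section 9.6 offers the trigger as an example of poor retention, and a share computed only among retained women would not show retention at all. On that reading, two late women out of 64 at week 24 could flag a trial whose drop-out is acceptable, which hardly fits a rule meant for severely compromised retention. A fix would cost only wording.

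The arithmetic stands, and so does the point that denominator, visit and timing are not written down. The consequence does not.

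- The tight case is the week-24 mail-in assessment, which has no lower limit and an allowance for postal return. Packets not back by day 189 will largely come from women already counted as lost, so lateness on top of drop-out should be small there.
- At the clinic visits, where windows of plus or minus 6 days make lateness more plausible, the 20% limit leaves 12.5% slack. That slack is not unlimited: at exactly 20% drop-out, 85% on time would give 68%. But that combines the worst acceptable drop-out with 15% lateness, which is a fair reason for the monitor to look.
- A flag obliges nobody to stop. It prompts consideration, alongside the monitor's review of recruitment, visit adherence, data quality and safety (section 7.6).

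On the label, no decision uses the Expected retention row. The exploratory drop-out regression depends on drop-out being substantial (sections 9.4 and 9.8), and the futility example uses 70%. The 17% case has no stated consequence.

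**Conclusion.** No change is needed. The trigger and the drop-out table are complements, not contradictory figures. They pull apart only if three things hold together: the share is taken over all randomized women, it is judged at week 24, and late returns come on top of drop-out close to its limit. Then the allowance for lateness is 1.4% of retained women at 29% drop-out and 6.7% at 25%. At week 12 it is 12.5% at the acceptable limit and 17.6% at the Expected-row limit. Among women still in follow-up there is no overlap. The crossing probabilities of 35% to 65% at week 24 rest on assumed on-time shares and on drop-out at the edge of the Expected row.

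The missing denominator, visit and timing are details that the team and the monitor can settle when they report follow-up, by showing drop-out and timeliness separately for each visit. The double use of expected is a clerical matter on which nothing depends. Because the trigger only invites consideration, following the plan as written gives no wrong result.

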## 9.7 Outcomes

### 9.7.1 Feasibility Outcomes

The feasibility of recruiting and randomizing middle-aged and older women with urinary incontinence into a randomized trial of yoga therapy versus physical conditioning will be examined by calculating the average number of participants recruited and randomized per month and per recruitment wave. It is assumed that the study team will need to recruit and randomize 15 to 30 women in each 3-month enrollment wave to confirm ability to assemble a class size of 8 to 15 women per group per wave in a future full-scale trial.

The feasibility of retaining participants in this trial design will be assessed by monitoring rates of drop-out or loss-to-follow-up over 8 and 12 weeks of treatment as well as during the 12-week post-treatment follow-up period. Drop-out rates in both treatment groups are expected to increase over time (i.e., to be greater at 12 weeks than at 8 weeks), but remain less than 20% after 12 weeks of treatment and less than 30% at 12 weeks of post-treatment follow-up.

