#### **4.3 Study Enrollment Procedures**

Recruitment: Participants will be recruited from the greater San Francisco Bay area using a multi-component approach that has been employed successfully in past clinical trials led by the investigators. This includes community-based media efforts (newspaper and radio advertisements, notices posted in community and senior centers, mass community mailings), recruitment from a database of women who have given permission to be contacted for women’s health research studies based at the University of California San Francisco, and posting of recruitment fliers in clinician offices (such as general internal medicine, geriatrics, gynecology, or alternative medicine).

Recruitment will be organized in waves to assemble successive cohorts of women who are confirmed to meet all eligibility criteria and who are available to attend upcoming group yoga or physical conditioning classes. Based on past experience, the investigators assume that three waves will be needed to recruit and randomize at 60 eligible participants, with up to three months of recruitment required per wave, and 15 to 20 eligible women randomized in each wave. This will allow for a minimum of ~8 women taking part in each class series in each intervention group.

Screening: Preliminary eligibility will be determined by research coordinators through a Screening Telephone Interview followed by an in-person Screening Clinic Visit. During the Screening Telephone Interview, coordinators will follow a standardized screening interview script to assess preliminary eligibility related to age, gender, incontinence history, and exclusionary conditions and medications and document reasons for ineligibility on the screening interview form (see section 6.2.3, Screening Procedures, for more detail). Candidates who appear preliminarily eligible at the end of the screening telephone interview will be scheduled to attend an in-person Screening Clinic Visit. After providing written informed consent at this visit, women will undergo more detailed assessment of incontinence symptoms, use of clinical incontinence therapies, exclusionary medical conditions, exclusionary medications, urine dipstick and pregnancy testing (for women of childbearing potential), and brief physical function assessment (see description of study procedures below), with reasons for eligibility or ineligibility documented on the screening clinic intake form.

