## **9.3 Intervention Assignment Procedures**

Randomization to the yoga therapy or physical conditioning control group will be performed by computer algorithm, with proof of eligibility required before assignment. Randomization will be implemented using randomly permuted blocks of sizes 2 and 4, and will also be stratified by clinical type of incontinence (i.e., stress, urgency, or mixed), to ensure adequacy of randomization within types. To avoid manipulation, standard allocation concealment procedures will be followed. A study analyst will prepare sealed, opaque envelopes containing group assignment, numbered consecutively with the randomization sequence numbers. At the baseline visit, when eligibility and incontinence type have been confirmed, coordinators will enter the date, participant name, and study ID in the randomization log and select the next numbered envelope to determine group assignment. All envelopes will be retained for review; randomization dates and times should follow the order of the sequence numbers, providing a check on validity. Although participants cannot be blinded to treatment assignment (due to the behavioral nature of the intervention), diary and questionnaire data used to evaluate the primary and secondary efficacy outcomes will be abstracted by blinded analysts.

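### The Aim 1 wave target starts one woman too low for two classes of 8, and the 9.7.1 feasibility outcome averages wave totals without counting women per group

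*Combined protocol and SAP*

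**What the plan says.** Aim 1, expected outcome 1: "We expect to recruit and randomize 15 to 30 women in each 3-month enrollment wave", in order to show that a future full-scale trial could fill classes of 8 to 15 per group in each wave. Section 9.4 has the same target ("The investigators plan to recruit and randomize 15 to 30 women in each 3-month enrollment wave"), and section 9.7.1 repeats it ("15 to 30 women in each 3-month enrollment wave to confirm ability to assemble a class size of 8 to 15 women per group"). In all three places the class minimum of 8 carries no qualifier.

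Section 4.3 gives the working plan for this pilot as "15 to 20 eligible women randomized in each wave", and adds: "This will allow for a minimum of ~8 women taking part in each class series in each intervention group". The lower figure is again 15, but here the class minimum is approximate.

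Allocation is 1:1. Section 9.3: "Randomization will be implemented using randomly permuted blocks of sizes 2 and 4, and will also be stratified by clinical type of incontinence". Wave is not a stratification factor. Section 6.2.4 has the scheme drawn up before recruitment starts, with coordinators taking the next numbered envelope for the woman's incontinence type.

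The recruitment outcome in 9.7.1 is the mean number of women enrolled, by month and by wave. Section 9.8 adds a descriptive summary for each wave. Neither section names a count per group.

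**The concern.** The objective concerns class size in each group, but the target and the outcome concern the wave total. The two agree only if the total is large enough and the split is close to even. At the stated lower end the total is too small for any split to work. At 16, and again at 30, one woman more in one group than an even split puts a class outside the range.

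Averaging adds a second gap. Waves of 10 and 22 average (10 + 22)/2 = 16, which lies inside 15 to 30, yet 10 women cannot fill two classes of 8.

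At stake is the recruitment half of Aim 1, whose purpose is to plan waves for the full-scale trial. A pilot could report an average inside the stated range while one class in a wave was below the stated minimum. The low end is realistic, because 4.3 plans for 15 to 20 women per wave. These counts are also taken at randomization, before any of the drop-out that 9.4 accepts (below 20% at 12 weeks).

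**Working it through.** **The plan's own figures.** Under an exact 1:1 split the wave total is 2 × class size: 2 × 8 = 16 and 2 × 15 = 30. The upper figure reproduces. The lower one is stated as 15, one fewer.

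**Splits that work.** For a wave of N women, with n in one group and N − n in the other, both lie in 8 to 15 when max(8, N − 15) ≤ n ≤ min(15, N − 8).

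- N = 15: 8 ≤ n ≤ 7, which is impossible.
- N = 16: n = 8 only.
- N = 18: n = 8 to 10.
- N = 20: n = 8 to 12.
- N = 26: n = 11 to 15.
- N = 28: n = 13 to 15.
- N = 30: n = 15 only.

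**How often the split works.** From the protocol: 1:1 allocation, three strata, permuted blocks of 2 and 4, no stratification by wave. Not stated, so assumed and varied:

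- block mix: half and half, all 2s, or all 4s;
- stratum shares: equal thirds, 45/45/10, or 50/50/0 (an almost empty mixed stratum is plausible, since 4.1 defines mixed type as an exact tie);
- open blocks carry over from one wave to the next, the natural reading of 6.2.4.

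Simulation of 40,000 three-wave trials for each of the nine settings gives this share of waves with both groups in 8 to 15 (lowest to highest setting):

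| Women in wave | Average over three waves | Any single wave |
|---|---|---|
| 15 | 0 | 0 |
| 16 | 0.406-0.648 | 0.358-0.750 |
| 18 | 0.877-0.980 | 0.834-1.000 |
| 19 | 0.956-1.000 | 0.936-1.000 |
| 20 | 0.986-1.000 | 0.979-1.000 |
| 24 | 0.999-1.000 | 0.999-1.000 |
| 26 | 0.987-1.000 | 0.980-1.000 |
| 28 | 0.875-0.979 | 0.833-1.000 |
| 30 | 0.399-0.645 | 0.351-0.751 |

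The first wave does best because every block starts fresh. If blocks restarted at each wave, all waves would behave like the first: about 0.49 to 0.75 at 16 or 30.

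**Hand check of the top of the range** (N = 16, all blocks of 2, two equal strata). In wave 1, both stratum counts are even with probability 1/2, and the split is then exact. Otherwise both are odd, each stratum is one out, and the two cancel half the time: 0.5 + 0.5 × 0.5 = 0.75. In later waves, both strata start with open blocks or both with closed ones, each with probability 1/2. With even counts and open blocks, each stratum is out by −2, 0 or +2 with probabilities 1/4, 1/2, 1/4, so the two cancel with probability 2 × 1/16 + 1/4 = 3/8. This gives 0.5 × 0.5 + 0.5 × (0.5 + 0.5 × 3/8) = 0.594. The three-wave average is (0.75 + 2 × 0.594)/3 = 0.646, against 0.648 simulated.

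**Size of the misses.** At 16 or 30, both groups are within one woman of the range (7 to 16) in about 83-100% of waves.

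**The case against.** The case for leaving this alone has weight. Half of 15 is 7.5, and 4.3 writes the minimum as approximate, so 15 looks like rounding. Section 5.1 calls 8 to 15 an expected class size, and nothing in the documents cancels or merges a class of 7. The wave target is worded as an expectation, a plan or an assumption. Recruitment has no graded adequacy table of the kind that 9.4 and 9.5 give for retention and adherence. Section 9.8 summarizes each wave, so a 15-woman wave would be visible. The target also looks ahead to a full-scale trial whose randomization is not specified here and could balance groups within waves.

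Most of this stands, and it limits the point to a minor one. It also rules out calling the wave target a formal decision threshold. It does not repair the lower bound, because Aim 1, 9.4 and 9.7.1 give 8 without a qualifier and 15 women cannot make two classes of 8 under any randomization. Nor does it supply the missing per-group count.

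A reader might infer more: that the criterion cannot show class assembly at all, or that 16- and 30-woman waves fail more often than not. The documents do not support either reading. Failures lie at the edges of the range, and whether the share at 16 or 30 is above or below one half turns on block mix, stratum shares and carry-over, none of which is stated.

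**Conclusion.** Wrong as written, and minor. The lower bound of 15 is at least one woman short in Aim 1, 9.4 and 9.7.1, and 4.3 uses the same figure. This part is arithmetic and needs no assumption. At exactly 16 or 30 both groups are in range in roughly 40-65% of waves on average, given carry-over of open blocks and the assumed block mixes and stratum shares. Totals of 20 to 26 succeed almost always. Independently of any simulation, an average wave total does not measure the class size per group that the objective names.

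It would also be tempting to replace the range with 18 to 28 and claim at least 90% assurance. That does not hold after the first wave: with three populated strata and a half-and-half or all-4 block mix, the later-wave figures at 18 and 28 are about 0.83 to 0.89. A cap of 28 would also score good recruitment as failure.

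**What to change.** In Aim 1, 4.3, 9.4 and 9.7.1:

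- Restate the lower bound as at least 16 women per wave, and note that about 18 to 20 is needed for both groups to reach 8 reliably.
- Keep the upper figure as a planning limit set by class capacity. Exceeding it should not count against feasibility.
- Assess class assembly by the number randomized per group in each wave, summarized as the share of waves with at least 8 in both groups, alongside the average wave total. The average still describes recruiting capacity, and the per-group count describes the classes.

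The cost is wording in four places and one extra line in the feasibility table. The stated lower recruiting target becomes slightly less favourable. Randomization and enrollment do not change.
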